## **7.17. Survival and Long-Term Follow-Up**

Each patient will be followed for survival and information about subsequent anticancer therapy every 12 weeks (3 months)  $\pm$ 14 days after patient's final protocol treatment with nivolumab, relatlimab or ipilimumab (whichever occurs last) until death, termination of the study, patient withdraws consent, or for a maximum of 2 years after the patient's final protocol-indicated treatment – whichever comes first. Contact can be made via clinic visit, chart review, obituary or similar observation (e.g. Social Security death index), or by telephone. Outside of this intended schedule, the sponsor-investigator and/or BMS may also request that survival data be collected on all treated subjects. At that time of this request, each subject will be contacted by similar means to determine their survival status unless the subject had withdrawn consent for all contact.

## **8. STUDY PROCEDURES**

### **8.1. Informed Consent**

Informed consent must be obtained before any study-specific screening assessments are performed. Screening assessments are to be performed within 14 days prior to Day 1 of Cycle 1 unless otherwise noted (e.g. baseline CT or MRI scan allowed up to 28 days prior to initiating Cycle 1, Day 1 treatment). Assessments performed as standard of care within the screening window may be used for screening. Baseline characteristics include but are not limited to: demographics, medical and surgical history, extent of disease, prior anti-cancer treatment, and tumor histology.

### **8.2. Physical Examination and ECOG Performance Status**

Physical examination and assessment of Eastern Cooperative Oncology Group (ECOG) performance status to be performed within 14 days prior to initiating protocol treatment; on Cycle 1, Day 1 (unless previously completed  $\leq$  7 days prior to a patient's first dose of protocol-indicated treatment), and at additional time points as outlined in [Section 7](#).

### **8.3. Vital Signs**

Vital signs to include: Heart rate (HR), blood pressure (BP), and temperature (oral or tympanic).

On each day of treatment with nivolumab/relatlimab or nivolumab/ipilimumab, Pre-Dose and Post-Dose vitals must be respectively recorded  $\leq$ 30 minutes prior to the start treatment, and  $\leq$ 30 minutes after the end of each separate treatment; thus:

- On Day 1 of each cycle in *Arm A*, a minimum of 3 sets of vital signs are scheduled to be recorded: Pre-nivolumab, Post-nivolumab and Post-relatlimab.
- In *Arm B*, on Day 1 of each of the first four cycles, a minimum of 3 sets of vital signs are scheduled to be recorded: Pre-nivolumab, Post-nivolumab and Post-ipilimumab. For *Arm B* cycles 5 onward, a minimum of 2 sets of vital signs are scheduled to be recorded: Pre-nivolumab and Post-nivolumab.

### **8.4. Body Weight**

Weight is measured at screening, prior to every dose of study treatment; and at the EOT, 30-day and 100-day Follow-up visits.

Patient's body weight must be measured *at least* on the *same day* in which every dose of nivolumab, relatlimab, or ipilimumab is administered to the patient.

**In *Arm B*: Each of the first 4 doses of nivolumab and ipilimumab (scheduled for administration on Day 1 of Cycles 1-4) must be adjusted if patient's body weight changes  $> \pm 10\%$  from the weight used to calculate the dose.**

### **8.5. Review of Concomitant Medications and Adverse Events**

Review and capture of all concomitant medications will be performed at each visit as indicated in [Section 7](#). Concomitant medications include prescription medications and over-the-counter preparations used by a patient within at least 14 days prior to first dose of protocol-defined

---

treatment and continuing through at least the 30-day Follow-Up study visit (or until initiation of subsequent anticancer therapy). Adverse events will be collected as detailed in protocol [Section 13](#).

### **8.6. Complete Blood Count (CBC) with Differential**

Local hematology results at time points indicated in Section 6.1 to include white blood cell count with differential, hemoglobin, hematocrit, and platelet count.

### **8.7. Blood Chemistry**

Local blood chemistry results at time points indicated in [Section 7](#) to include sodium, potassium, chloride, bicarbonate or carbon dioxide, blood urea nitrogen (BUN), creatinine, glucose, total bilirubin, AST, ALT, alkaline phosphatase (ALP), calcium, albumin, total protein; magnesium and phosphorus.

### **8.8. Additional Labs**

Blood draws for additional local laboratory assessment of LDH, TSH, free T3, free T4, cortisol, troponin-I, CK, and CK-MB at time points indicated in [Section 7](#). Designation of “reflexive” in Section 7 indicates assessment of free T3 and free T4 only when TSH is not within normal range. ACTH, amylase and lipase done as clinically indicated per judgment of the investigator.

### **8.9. ECG**

For patients in Arm A: Standard 12-lead electrocardiogram (ECG), single tracing, using local site equipment completed during screening for all patients. Additional single tracing ECGs done prior to treatment on days as indicated in [Section 7.2](#). Additional ECGs as clinically indicated per patient's study physician.

The corrected QT interval (QTc) will be calculated using the method of Fridericia (QTcF), where QTcF equals the QT interval divided by the cube root of the RR interval:

$$QTcF = \frac{QT}{\sqrt[3]{RR}}$$

Note: During screening, as part of eligibility verification, QTcF > 480 msec is an exclusionary criterion ([Section 5](#)).

### **8.10. Pregnancy Test**

For women of childbearing potential (WOCBP): Serum pregnancy test required during screening; and either serum or urine pregnancy test required ≤ 72 hours prior to first dose of protocol-indicated treatment (unless serum pregnancy test during screening was already done ≤ 72 hours prior to initiating c1d1 treatment), and at the EOT and 30-day Follow-up visits.

See [Appendix 4](#) for study required contraception and definition of WOCBP.

### **8.11. Disease Assessment by CT/MRI**

Baseline evaluation of disease status by Computed Tomography (CT) and/or Magnetic Resonance Imaging (MRI) ≤ 28 days prior to initiating protocol treatment on Cycle 1, Day 1.

---

Baseline and subsequent scans to include imaging of the chest, abdomen, and pelvis and CT and/or MRI of the brain. Additional sites of known or suspected disease should be imaged during screening and subsequent scans.

*Re-scanning to occur every 12 weeks* (minus 1-7 days) after initiating protocol treatment on Cycle 1, Day 1. The minus 1-7 day scan window is intended for flexibility in scheduling.

Additional disease evaluations or increased scan frequency may be performed according to the medical judgment of the patient's study physician, in accordance with the following: In the event of suspected Progressive Disease (PD), a CT/MRI is to be performed as soon as possible. In the event of a Complete or Partial Response (CR/PR), a confirmatory CT/MRI is to be performed no earlier than 28 days after the first assessment of CR/PR.

At End-of-Treatment, CT/MRI required only if the previous CT/MRI was done >28 days before.

At the 1M F/U Follow-Up visit, CT/MRI required only if disease progression was not already documented by CT/MRI done before, during or after the prior EOT visit.

If a patient discontinues the study for reason other than progressive disease confirmed by CT or MRI (e.g. adverse event), then CT or MRI scans involving sites of known or suspected disease must be continued (if clinically feasible) every 12 weeks ( $\pm$  7 days) for 12 months and then approximately every 24 weeks ( $\pm$  4 weeks) thereafter, relative to date(s) of prior scanning, until disease progression is confirmed by imaging.

If the patient initiates treatment in another clinical trial, then any continuing scans done for this trial may terminate.

## **8.12. Required Baseline Tumor Tissue**

Archival tissue [paraffin block(s) or unstained slides from paraffin block(s)] from the primary tumor and/or a metastatic site must be available prior to initiating treatment, or patient must be willing to undergo a fresh pre-treatment standard of care tumor biopsy. Within 28 days prior to initiating treatment, the screening team must have documentation that an archival or fresh tumor specimen has been requested from a local or outside facility. Physical possession and centralized testing of requested tissue is required prior to initiating study treatment because all patients in this study are being stratified by MHC-II status, based on centralized testing performed at Vanderbilt.

## **8.13. Fresh Tumor Biopsy**

Fresh biopsy of lesion amenable to safe biopsy from a primary lesion or metastatic site, performed approximately 6 weeks following initiation of protocol-indicated treatment:

- Arm A: Fresh biopsy on Cycle 2, Day 15 ( $\pm$ 7 days)
- Arm B: Fresh biopsy on Cycle 3, Day 1 ( $\pm$ 7 days).

Note that research blood is also scheduled for collection on these days, and with similar  $\pm$ 7 day flexibility, in order that the research blood draws are ideally obtained on the same day as the on-study fresh biopsy (and ideally PRIOR to the biopsy procedure).

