### **3.7. Rationale for Primary Endpoint**

The primary endpoint for this study is change in CD8+ T cell infiltration. Several studies have demonstrated influx of CD8+ T cells as demonstrating immunologic recognition and targeting, and as an early surrogate for treatment response. For example, one study demonstrated that expression of CD8 in early on-treatment biopsies was completely non-overlapping in responders compared with non-responders. Thus, this metric can serve as an accurate surrogate of immunologic recognition and tumor responses, and is likely more reliable than a metric such as complete pathologic response, particularly in the setting of bulky tumors that may require additional time for complete regression. In addition, in this signal finding phase II study, we are evaluating two arms with likely active treatments in parallel, rather than comparing these interventions. Sample size is further based on doubling of CD8+ T cell infiltration from analysis of responding patients in two studies, with a standard deviation of 1000.

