### **18.2. Sample Size and Power**

The primary endpoint for this study is change in GZMB+ CD8+ T cell infiltration. A total sample size of 36 with 18 in each arm will provide 83% power to detect a difference in mean activated CD8+ T cell density change of one standard deviations (e.g., 1 SD=1000 counts/mm^2 is roughly the effect size for doubling T cell count), with a two-sided significance level of 0.05. Assuming a 10% dropout rate, a total number of 40 patients is planned for enrollment in the study to ensure the study has adequate statistical power for the primary analysis.

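### The primary analysis can use only patients with a week-6 biopsy, and biopsies lost because of outcome may bias the result in either direction; the plan defines no evaluable set and no handling of missing biopsies.

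*Combined protocol and SAP*

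**What the plan says.** Section 18.2 states: "The primary endpoint for this study is change in GZMB+ CD8+ T cell infiltration". The only tissue scheduled on treatment is the biopsy in Section 8.13, at Cycle 2 Day 15 in Arm A and Cycle 3 Day 1 in Arm B, each within 7 days either way, taken as "Fresh biopsy of lesion amenable to safe biopsy from a primary lesion or metastatic site".

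On size, Section 18.2 plans 36 patients, half of them in either arm, and claims that this number "will provide 83% power to detect a difference in mean activated CD8+ T cell density change of one standard deviations". The test is two-sided at 0.05. For losses, the same section makes one allowance: "Assuming a 10% dropout rate, a total number of 40 patients is planned for enrollment in the study".

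Section 18.4 plans a t-test between groups with the Wilcoxon rank sum test as fallback, and a linear regression of post-treatment density on MHC-II status adjusted for baseline density. Neither Section 18 nor any other section defines an analysis set for the primary endpoint, a rule for a missing biopsy or absent tumour, or a sensitivity analysis. Section 5.4 counts evaluable patients, but its replacement rule concerns evaluability for toxicity.

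**The concern.** A patient with no week-6 sample has no outcome in any of the planned models, so the primary result will describe biopsied patients whether or not the plan says so. Some reasons for having no sample are themselves outcomes. Patients who die or progress early are likely to be poor responders, while a patient with no tumour left is a very good one.

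Section 3.7 supplies the link to the endpoint. It cites a study in which CD8 expression in early on-treatment biopsies did not overlap between responders and non-responders. On that premise, a biopsy lost to progression or regression removes a value from one end of the distribution. Losing low values raises the observed mean, and losing high values lowers it.

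The schedule leaves room for such losses. Under Section 9.9 it runs until both drugs are permanently stopped, and the end-of-treatment list in Section 7.15 contains no biopsy. Eligibility (Section 5.1) requires a measurable lesion but not one that can safely be biopsied on treatment. At stake are the per-arm mean change and the powered contrast between arms.

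**Working it through.** **1. The plan's own figures.** Inputs from Section 18.2: 18 per arm, a difference of 1 SD, two-sided 0.05. For a two-sample t-test, df = 34 and noncentrality = sqrt(18 × 18 / 36) = 3.0, which gives 83.0% power and matches the stated 83%. Dropout: 36 / 0.9 = 40, which also matches. The powered analysis is therefore the between-arm comparison, and the 10% only restores the number of observations.

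**2. Bias of one arm mean, as a bound.** Assumptions: responders gain 1000 counts/mm2, non-responders gain 0, and the response rate is p = 0.58 (nivolumab plus ipilimumab, Sections 3.1 and 3.2). The true mean is 580. The fraction missing, m, is not in the documents; 10% and 20% are assumed.

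- All missing are non-responders: mean = 1000 × p / (1 − m). At 10%, 580 / 0.9 = 644 (+11%). At 20%, 580 / 0.8 = 725 (+25%).
- All missing are responders: mean = 1000 × (p − m) / (1 − m). At 10%, 480 / 0.9 = 533 (−8%). At 20%, 380 / 0.8 = 475 (−18%).

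**3. The same without response classes.** Bias = m × D, where D is the mean change in biopsied patients minus that in missing patients. D is assumed to be 0.5 to 1.5 SD in either direction. The SD is the plan's: "with a standard deviation of 1000" (Section 3.7).

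| Missing | Bias of arm mean, counts/mm2 |
|---|---|
| 10% | ±50 to ±150 |
| 20% | ±100 to ±300 |
| 30% | ±150 to ±450 |

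**4. The powered contrast.** Bias of B − A = mB × DB − mA × DA. Assume 20 enrolled per arm and |D| = 1 SD, with type I error and power from the noncentral t.

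| Missing A / B | Cause in the two arms | Bias (SD) | Type I error | Power for a true +1 SD |
|---|---|---|---|---|
| 10% / 10% | same | 0 | 5% | 83% |
| 10% / 10% | opposite | ±0.2 | 9.0% | 64.5% or 93.8% |
| 10% / 30% | same | ±0.2 | 8.4% | 58% or 90% |
| 10% / 30% | opposite | ±0.4 | 19.2% | 37% or 97% |

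**5. Precision, separately.** With 20 per arm, 20% missing leaves 16 and 78.1% power; 30% leaves 14 and 72.1%. Keeping 18 biopsied per arm needs 2 × 23 = 46 enrolled at 20% missing (18 / 0.8 = 22.5, rounded up) or 2 × 26 = 52 at 30% (18 / 0.7 = 25.7). Larger enrolment restores power but leaves m × D unchanged.

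**The case against.** The case against is substantial. Nothing in the documents states a biopsied-only analysis set, a missing-biopsy rate or a cause of loss. Several rules limit the losses:

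- Procedures continue during dose holds (Section 11), and stopping one drug of the pair does not end the schedule (Section 9.9).
- The first scheduled re-scan is at 12 weeks (Section 8.11), and treatment beyond initial progression is allowed under conditions (Section 9.8).
- Entry requires ECOG 0 or 1 and excludes life expectancy under 6 months (Sections 5.1 and 5.2), which makes death by week 6 less likely.
- Section 3.7 expects bulky tumours to need longer to regress completely, so few patients may have nothing to biopsy.

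The step 2 shifts of +64, +145, −47 and −105 are also modest beside the standard error of an arm mean, 1000 / sqrt(18) = 236, at about 0.2 to 0.6 of it. They assume that all missing patients fall in one class, and the 58% comes from a trial not selected on MHC-II.

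All of this stands as a limit on size. It does not supply a rule for the biopsies that are still missed.

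A reader might infer that the direction of any bias could never be checked. That goes too far: RECIST response, adverse events and discontinuation data are collected and would allow some comparison of patients with and without a biopsy. What is absent is a pre-specified comparison and a recorded reason for each miss.

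It is also fair that ranking every toxicity stop worst would be contestable, since immune toxicity does not imply low infiltration, and that per-arm tests alone would miss the powered contrast. The fix reflects both points.

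**Conclusion.** The point holds as a risk that the plan leaves unaddressed. As written, the primary analysis can include only patients with a week-6 biopsy, and losses tied to outcome may bias the mean change and the arm difference either way. There is no bias if missingness is unrelated to change, and the regression covers missingness explained by arm and baseline density alone. On the rationale in Section 3.7, neither condition can be taken for granted.

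The size is illustrative. The −18% to +25% range is a one-sided bound under assumed 10% to 20% missingness, and losses of opposite kinds within an arm would partly offset. For the arm difference, the effect runs from none (equal losses, same cause) to 0.4 SD with type I error of about 19% (assumed 10% against 30% missing, opposite causes, |D| = 1 SD).

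Two stronger readings are tempting. One is that the result is biased; the documents do not show that any biopsy will be lost for these reasons. The other is that losses will differ by regimen, from the background grade 3-4 rates of 59% and 10.2% (Sections 3.2 and 3.3). Those rates come from different populations and are not week-6 discontinuation rates. They make equal losses hard to assume but do not establish unequal ones.

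**What to change.** 1. In Section 18, define the set evaluable for the primary endpoint.
2. Add an eCRF field for the reason that a week-6 biopsy is missing: death or progression; toxicity; no residual tumour; no lesion safe to biopsy; refusal or administrative. Write down beforehand what counts as no residual tumour, since no scan is scheduled at week 6 and the study is open-label.
3. Pre-specify one rank-based sensitivity analysis on all treated patients, reported beside the complete-case result. Use a between-arm Wilcoxon rank-sum test, because that is the powered contrast, with per-arm signed-rank or sign tests as support. Rank death or progression worst and no residual tumour best. Run toxicity-related misses both ways, once as worst and once as best. Treat no safe lesion and refusal or administrative misses as missing.

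The cost is one field and one analysis, with no added patients or procedures. The rank result mixes clinical outcome with density and gives no mean in counts/mm2, so it supports the complete-case estimate and does not replace it.

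Separately, reconcile the 40 patients in Section 18.2 with Section 2, which stops accrual at 18 enrolled per arm. Under the latter the 10% allowance does not exist: 18 × 0.9 = 16.2, or about 16 per arm and 78.1% power.

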## **8.14. Biomarker and Pharmacodynamic (PD) Blood Samples**

Peripheral blood samples for exploratory analysis including biomarker and possible PD research to be obtained at time points indicated in [Section 7](#).

---

Note that 2 of these time points also correspond to days when fresh tumor biopsy is also intended (i.e. Cycle 2, Day 15 in Arm A; and Cycle 3, Day 1 in Arm B). To accommodate scheduling, a  $\pm 7$  day window for the fresh on-study biopsy is allowed; therefore, a similar  $\pm 7$  day window is also applicable to the research blood draws scheduled for these two time points, in order for the research blood to be collected ideally on the same day as the fresh biopsy (and ideally PRIOR to the biopsy procedure).

### **8.15. Handling of Biological Samples**

All biological samples to be analyzed locally will be collected and handled according to local institutional practices. All biological samples to be analyzed centrally will be collected and handled according to a provided laboratory manual. Retention time for biologic specimens will be specified in the laboratory manual.

## **9. PROTOCOL TREATMENT**

### **9.1. Dose Summary**

This is a phase 2, open-label, two-arm study in patients with locally advanced/unresectable or metastatic melanoma, evaluating the efficacy of either nivolumab plus relatlimab against MHC-II positive tumors (Arm A); or nivolumab plus ipilimumab against MHC-II negative tumors (Arm B). The dose summary for each respective study arm is presented below in **Table 3** and **Table 4**:

**TABLE 3: Dose Summary, Arm A, MHC-II Positive**

ARM A: MHC-II (+)	4 week cycles		Comments: Arm A All Cycles = 28 days (4 weeks) per cycle
	Cycles 1+	DAY 1	
Nivolumab	480 mg		30 minute i.v. infusion
Relatlimab	160 mg		60 minute i.v. infusion Relatlimab infusion to be started AFTER completion of nivolumab infusion.

**TABLE 4: Dose Summary, Arm B, MHC-II Negative**

ARM B: MHC-II (-)	3 week cycles	4 week cycles	Comments: Arm B Cycles 1-4 = 21 days (3 weeks) per cycle Cycles 5+ = 28 days (4 weeks) per cycle
	Cycles 1, 2, 3, and 4 DAY 1	Cycles 5+ DAY 1	
Nivolumab	1 mg/kg	480 mg	30 minute i.v. infusion
Ipilimumab	3 mg/kg		90 minute i.v. infusion Ipilimumab infusion to be started AFTER completion of nivolumab infusion.

Stratified by MHC-II status (either positive or negative) of baseline tumor tissue, participants will receive one of the following regimens:

- **Arm A (MHC-II positive):**
  - nivolumab 480mg IV + relatlimab 160mg IV q4w.
- **Arm B (MHC-II negative):**
  - nivolumab 1mg/kg IV + ipilimumab 3mg/kg IV q3w x4 (i.e. 4 total doses of nivolumab, and 4 total doses of ipilimumab); then
  - nivolumab 480mg IV q4w.

---

Every effort should be made to target infusion timings to be as close as possible to the scheduled duration. But given the variability of infusion pumps, time windows of  $\pm 10$  minutes for the scheduled duration of infusions are permitted. (Additionally, prolongation of infusion duration for the purpose of managing suspected or actual adverse event such as infusion reaction will not be considered a protocol deviation.)

In Arm B, doses of nivolumab and ipilimumab administered on a mg/kg basis (i.e. all those given prior to initiation of flat-dose nivolumab scheduled to begin in Cycle 5 of Arm B) will be determined by measuring the patient's weight in kilograms on the day of dosing, prior initiation of nivolumab/ipilimumab.

If the patient's weight on the day of dosing differs by  $> \pm 10\%$  from the weight used to calculate a dose based on mg/kg, then doses of nivolumab and ipilimumab must be recalculated prior to administration.

In Arm B, unless otherwise specified (e.g. by established institutional practice), all calculated doses based on mg/kg may be rounded up (or down) to the nearest milligram; and a  $\pm 5\%$  variance in the calculated total dose will be allowed for ease of dose administration.

## **9.2. Antiemetic Premedication**

Administration of established institutional standard premedication prior to infusion is allowed, however it is recommended that antiemetic medications should not be routinely administered prior to dosing of drugs. See [Section 11.5](#) for subsequent premedication recommendations following a study drug-related infusion reaction.

